Supragingival calculus on the lingual surfaces of the six mandibular anterior teeth will be scored using the Volpe-Manhold calculus index (CI).³⁶ Supragingival calculus height in three defined planes on the lingual surface of each tooth will be measured using a periodontal probe. The measurements will be added and a mean subject score calculated.

Plaque will be scored based on the Turesky modification of the Quigley—Hein Plaque Index (PI).³³ A score of 0 – 5 will be assigned to six sites of each tooth (distobuccal, buccal, mesiobuccal, distolingual, lingual, mesiolingual) following the use of a disclosing solution. The Plaque Index for the entire mouth will be determined by dividing the total score by the number of surfaces examined.

Teeth with gross caries and third molars will not be scored. A complete periodontal examination will be performed for all subjects that meet the inclusion criteria. A panoramic radiograph will be taken for all subjects who do not have full mouth radiographs within the last year. Safety assessments will be made at each measurement visit.

Visit 2 will occur within four weeks of Visit 1. For this relatively small clinical study for which there are two centers and three treatments, subjects will be assigned treatments through the process of minimization to assure a balance in the number of subjects in each treatment group: Group 1 SM, Group 2 CHX or Group 3 PL. PL will be identical to SM, except it will not contain cetylpyridinium chloride, zinc chloride and sodium chlorite. Each group will consist of approximately 25 subjects. All subjects will be given a complete dental prophylaxis to remove plaque, calculus, and stain. Written and verbal oral hygiene instructions will be given that will includ a regular regimen of brushing twice daily and flossing daily. All subjects will be assigned a commercially available ADA accepted toothbrush and dental floss. They will be given a three-

week supply of the assigned mouth rinse with written and verbal instructions for use. Subjects will be instructed not to have their teeth professionally cleaned prior to study completion.

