All mouth rinses will be in a plain package and dispensed by the faculty investigators. The package will be labeled with a code to indicate the product. Only the faculty investigators will have access to the code information. Group assignment will be performed by one of the investigators who will use the process of minimization and will not be aware of the periodontal health of subjects. Directions for use are contained in the package. The examiners will not see the product. The examiners will give instructions for mouth rinse use, but they will not be aware which rinse the subjects are using. Each product will contain two solutions which are mixed prior to use.

Subjects will be examined again at visit 3, three weeks after visit 2. All clinical measurements will be repeated. Each subject will return the unused rinse. Additional rinse will be given to each subject after visit 3 for use until the final visit. Compliance will be determined by regulating the amount of rinse dispensed on a 3 week basis and by the measurement of any unused rinse (compliance defined as percentage of product used).

Subjects will be examined again at visit 4, three weeks after visit 3. Clinical measurements will be repeated. Each subject will return the unused rinse. Compliance will be determined by the measurement of any unused rinse at the end of the study. Subjects will be given a Taste Perception Survey to answer questions about their experience with the mouth rinse.

Following the study, the subjects will be treated by their provider's discretion. Subjects can withdraw from the clinic trial at any time without providing reason. The investigators can also withdraw subjects at any time due to protocol irregularity. All instances of withdraw will be documented.

Intra-Examiner Calibration

Intra-examiner calibration will be completed prior to beginning the study. Three examiners ([name]) will make original and repeat determinations of values for four teeth in ten subjects for each of four indices. A kappa value will be determined for each original and repeat determination, and the average kappa value will be determined for the four teeth for each index for each examiner. For an examiner to be considered calibrated, average kappa values for each index have to be between 0.81 and 1 (almost perfect agreement).

Data Analysis

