The primary outcome measures are gingivitis and plaque. Secondary outcome measures are tooth discoloration, taste perception, malodor and calculus. For each outcome measure, a single value will be calculated for each subject—that is, the subject is the unit of measurement for analyses.

Analyses will be based on intention to treat (with randomized intervention). Sensitivity analyses will be based on as treated analyses. To test for differences among and between treatments, we will

use repeated measures analysis of variance (ANOVA) with treatment and location as the between-group factors and one within-subject (repeated-measures) factor with 2 levels: (1) measurements at visit 3 and (2) measurements at visit 4. For these analyses, we will use multivariate analysis of variance (MANOVA), which does not require the assumptions of compound symmetry (homogeneous pooled within-group variances and across-subjects covariances) and sphericity (orthogonal components). Post-hoc testing will be performed with the Tukey honestly significant difference ([HSD] test.

Sample-size calculation and power analysis (treatment effect of Smart Mouth ACF): One goal of the proposed study is to test the null hypothesis that the mean gingival score for Smart Mouth ACF is equal to the mean gingival score for the placebo (control). With alpha (the criterion for significance) set at 0.05, a 2-tailed test (which means that an effect in either direction will be interpreted), and a sample size of 20 and 20 for the two groups, the study will have a power of 99.9% to yield a statistically significant result. This computation is based on data from Ayad et al (2011), with the assumption that the mean difference is 0.44 (corresponding to means of 2.03 versus 1.59) and a common within-group standard deviation of 0.27 (based on SD estimates of 0.22 and 0.31). We assume that this effect size is reasonable, in the sense that an effect of this magnitude is anticipated in this field of research. We could report an observed difference of 0.44 with a 95.0% confidence interval of 0.27 to 0.61. Based on plaque scores given in Ayad et al (2011) and a sample size of 20 in each group, we would have a power >99.9% to demonstrate a treatment effect for Smart Mouth ACF. Our intent is to enroll 25 subjects into each group. Our sample-size calculations assume a 20% dropout rate. We, however, anticipate that the dropout rate will be less than 10%.

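### Examiners are checked only against themselves and examiner is not in the model, so some between-examiner difference can enter the error term: a modest loss of precision, felt mainly in the chlorhexidine equivalence comparison

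*Combined protocol and SAP*

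**What the plan says.** Under Intra-Examiner Calibration the plan says "Intra-examiner calibration will be completed prior to beginning the study". Three examiners "will make original and repeat determinations of values for four teeth in ten subjects for each of four indices", and for an examiner to count as calibrated, "average kappa values for each index have to be between 0.81 and 1". Kappa is computed separately for each examiner. The document describes no comparison of one examiner with another, no reference examiner and no recalibration during the study.

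The study runs at two centers (Materials and Methods). Under Data Analysis the repeated-measures model has "treatment and location as the between-group factors" and visit (3 and 4) as the within-subject factor. It has no examiner term. Both primary outcomes, gingivitis and plaque, are scored by examiners.

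The document does not say which examiner works at which center, whether a subject keeps the same examiner across visits, or whether minimization takes account of examiner. It does say that the examiners do not see the product and do not know which rinse a subject uses.

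**The concern.** Repeating one's own scores tests repeatability. It does not test whether two examiners score at the same level. A consistently strict examiner and a consistently lenient one can both reach a kappa of 1 against themselves, and the analysis then pools their scores as interchangeable.

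The location factor removes whatever part of an examiner difference coincides with center. With three examiners and two centers, either some center has two or more examiners or an examiner works at both. In either case at least one examiner contrast lies outside the model. It then adds to the error variance and, if a subject changes examiner between visits 3 and 4, to the apparent within-subject change.

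The comparison with least room for extra variance is equivalence with chlorhexidine, where the margin is 0.20 GI points.

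**Working it through.** **Inputs from the Data Analysis section**
- SM versus placebo: difference 0.44, SD 0.27, 20 per group, two-sided alpha 0.05, stated power 99.9%.
- SM versus chlorhexidine: true difference 0, SD 0.25, margin 0.20, 21 per group, one-sided alpha 0.05, stated power 81.7%.

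**Assumptions, because the documents give no between-examiner figure**
- One center has one examiner and the other has two. The centers are of equal size, and the two examiners at the second center each score half of its subjects.
- The offset D between those two examiners is 0.1, 0.2 or 0.3 GI points.
- Each subject has one examiner throughout.
- The planning SDs do not already contain this variation.

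**1. Reproduce the stated powers.**
- SM versus placebo: standard error = 0.27 × √(2/20) = 0.0854, and 0.44/0.0854 = 5.15. The noncentral t with 38 df gives 99.9%, as stated.
- Equivalence: standard error = 0.25 × √(2/21) = 0.0772, and 0.20/0.0772 = 2.59. A single one-sided t test with 40 df gives 81.7%, as stated. Two one-sided t tests at 0.05 each, which the two-sided equivalence hypothesis calls for, give 63%. The gap between 81.7% and 63% is a separate matter and has nothing to do with examiners. Both starting points are carried forward.

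**2. Added variance.** A 50:50 split between two examiners who differ by D adds D²/4 to the variance at their center. Averaged over two equal centers, the addition is D²/8, so SD(new) = √(SD² + D²/8).

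| D | D²/8 | SD from 0.25 | SD from 0.27 |
|---|---|---|---|
| 0.1 | 0.00125 | 0.252 | 0.272 |
| 0.2 | 0.00500 | 0.260 | 0.279 |
| 0.3 | 0.01125 | 0.272 | 0.290 |

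**3. Power with the inflated SD.**

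| D | SM vs placebo (n = 20) | Equivalence, plan's one-sided method (n = 21) | Equivalence, two one-sided tests (n = 21) |
|---|---|---|---|
| 0 | 99.9% | 81.7% | 63% |
| 0.1 | 99.9% | 81.0% | 62% |
| 0.2 | 99.8% | 79.0% | 58% |
| 0.3 | 99.7% | 75.8% | 52% |

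**4. A less favorable allocation.** If two examiners split every arm evenly across both centers, the full D²/4 is added and the SD rises from 0.25 to 0.255 / 0.269 / 0.292. With 21 per group, two one-sided tests give 61% / 53% / 41% and the plan's one-sided method gives 80.3% / 76.5% / 70.5%. SM versus placebo, at 20 per group, stays at 99.2% or more.

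**The case against.** The strongest counter-argument is about size. The primary SM versus placebo comparison has so much power that no offset examined here matters. The natural reading of three examiners at two centers is one plus two, and then location absorbs the between-center part. No document gives an examiner offset, and the planning SDs come from a cited study that may already include examiner variation. All of this stands, and it is why the one-plus-two allocation is the main case above.

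Three stronger readings are tempting but are not supported.
- *Bias in the treatment effect.* A reader might infer that examiner differences distort the treatment contrast. The examiners do not know the rinse, and the investigator who assigns groups does not know the subjects' periodontal health. Chance imbalance of examiners between arms is possible, but its SD at D = 0.3 is only about 0.03 (0.3 × 0.5 × √(2 × 0.25/10), with about ten subjects per arm at that center). That is the same noise already counted in the inflated SD.
- *Examiners will switch between visits.* The document is silent on this. Silence leaves the possibility open but does not show that it will happen.
- *Kappa is the wrong statistic.* A reader might note that calculus height "will be measured using a periodontal probe" and conclude that kappa has been misapplied. The calibration section names neither the four indices nor the weighting, so this is an inference. Nor is it shown that the rule passes a poor examiner on that account: if kappa is unweighted, a threshold of 0.81 is generally the stricter rule for ordinal scores. Calculus is also a secondary outcome.

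**Conclusion.** The gap is real and its consequence is limited. The calibration cannot detect a level difference between examiners, and the model cannot remove all of it if all three examiners score study subjects. What is lost is precision.

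For SM versus placebo the loss is negligible. For equivalence with chlorhexidine, in the one-plus-two allocation, an offset of 0.2 costs about 3 percentage points of power by the plan's own method and about 5 by two one-sided tests. An offset of 0.3 costs about 6 and 12 points. These figures rest on assumed offsets, on an even split at one of two equal centers, and on the planning SD not already including examiner variation. Where it does include some, the loss is smaller.

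The change is worth making because it is cheap and because an examiner who was not recorded cannot be added to the model afterwards.

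**What to change.** 1. Record the examiner at every scoring visit.
2. Keep each subject with one examiner at visits 1, 3 and 4.
3. Add examiner within location to the repeated-measures model.

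Items 2 and 3 belong together. A fixed examiner adds D²/4 to the variance of a subject's mean over visits 3 and 4, whereas independent 50:50 assignment at each visit would add D²/8. Without the model term, item 2 therefore does not help the visit-averaged contrast. It does prevent false within-subject change.

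4. Where the examiners score the same ten calibration subjects, report between-examiner agreement from those scores as well. The document does not say that the subjects are shared. If they are not, this step needs extra scoring and is no longer free.
5. If calculus height is one of the four indices, report an intraclass correlation for it.

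Items 1 to 3 cost scheduling, one recorded field and about one degree of freedom.

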The aim of this six-week double-blind, placebo-controlled clinical trial was to provide evidence of the clinical efficacy of SmartMouth Clinical DDS Advanced Oral Rinse (SM) in comparison with the efficacy of 0.12% chlorhexidine rinse (CHX) and a placebo rinse (PL). The outcomes included measures of plaque, gingivitis, tooth staining, calculus formation, patient compliance, and taste perception.

Materials and Methods:

A six-week, double-blinded, clinical study will be conducted on 80 subjects diagnosed with plaque induced gingivitis and/or chronic periodontitis. The study will take place at two centers: Saint Louis University Center for Advanced Dental Education (Site 1) and Southern Illinois University School of Dental Medicine (Site 2). The study was approved by the Institutional Review Boards (IRB #25867) at Saint Louis University and Southern Illinois University Edwardsville.

Subjects who sign the informed consent and medical history forms and meet the preliminary entrance criteria will be examined at baseline (visit 1). All participants will be informed of the nature of the study, its purpose, and any possible risks. Subjects will be informed as to the length of the study and the specific procedures that would be performed. Subjects will be informed that this was a voluntary study and that they are free to withdraw from the study at any time.

Gingival index (GI) will be measured using the Loe and Silness method.²⁴ The gingiva will be scored at six sites of each tooth (distobuccal, buccal, mesiobuccal, distolingual, lingual, mesiolingual) and given a score from 0 – 3. By adding the scores and dividing by the total number of sites, the GI for the patient will be obtained.

Sites with GI scores of 2 or 3 will be counted as bleeding. A whole mouth total Bleeding Score (BS) will be calculated by summing the number of bleeding sites and dividing by the number of teeth.

Extrinsic tooth stain will be scored on the facial surfaces of the eight incisor teeth using a modification of the Lobene tooth stain index (TSI).²³ Each incisor will be scored for stain area on a scale of 0-3. The sum of the stain scores for the subject will be used as that subject's stain score.

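### The stain score is a raw sum over eight incisors with no adjustment for unscored teeth; a mean per scored incisor would remove the gap (minor)

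*Combined protocol and SAP*

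**What the plan says.** Tooth discoloration is one of four secondary outcomes in the Data Analysis section: "Secondary outcome measures are tooth discoloration, taste perception, malodor and calculus".

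Materials and Methods describes how it is scored. Stain is assessed on the facial surfaces of the eight incisors with a modified form of a cited index. "Each incisor will be scored for stain area on a scale of 0-3". The scores are then added: "The sum of the stain scores for the subject will be used as that" subject's stain score. No denominator is given.

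Later in the same section, after the plaque index, comes a general exclusion: "Teeth with gross caries and third molars will not be scored". Nothing says what happens to the stain sum when one of the eight incisors falls under it.

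The other indices in Materials and Methods are scaled to what was scored:
- Gingival index: "By adding the scores and dividing by the total number of sites".
- Bleeding score: "summing the number of bleeding sites and dividing by the number of teeth".
- Plaque index: "dividing the total score by the number of surfaces examined".
- Calculus index: "The measurements will be added and a mean subject score calculated".

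**The concern.** A raw sum measures two things at once: how stained the teeth are, and how many teeth were scored. Two subjects with the same stain on every tooth get different scores if one of them has an incisor that was left out. The plan avoids this for every other index but not for stain.

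Stain matters to the trial's message. The Introduction names tooth staining as a side effect of chlorhexidine and says that rinses with cetylpyridinium chloride are not associated with it, so a stain comparison is likely to be reported. A score that depends partly on tooth count makes that comparison noisier. If the count differs between arms, it also shifts the comparison.

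**Working it through.** The plan gives no power or precision figure for stain, so there is no stated figure to reproduce. The check is arithmetic on the scoring rule.

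**Inputs**
- Eight incisors, each scored 0–3, summed (Materials and Methods).
- Teeth with gross caries not scored (Materials and Methods).
- 25 subjects intended per group, with 20% dropout assumed in planning (Data Analysis). This leaves 25 × (1 − 0.20) = 20.
- Number of subjects with an unscored incisor: not given.

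**Step 1: one subject.** Let *k* be the number of incisors scored and *m* the mean stain per tooth, taken as equal for scored and unscored teeth. The sum is *k·m*, against 8*m* for a full set. The shortfall is 1 − *k*/8.

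| Incisors scored | Maximum (3*k*) | Sum at *m* = 1 | Shortfall | Mean per scored incisor | Eight times the mean |
|---|---|---|---|---|---|
| 8 | 24 | 8 | 0% | 1 | 8 |
| 7 | 21 | 7 | 12.5% | 1 | 8 |
| 6 | 18 | 6 | 25% | 1 | 8 |

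Each unscored incisor costs (24 − 21)/24 = 12.5% of the full value. The mean per scored incisor does not move.

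**Step 2: one arm.** A subject with one unscored incisor lowers the arm mean by 12.5%/*n*, taking that subject's stain per tooth as average for the arm:
- *n* = 25: 12.5%/25 = 0.5%.
- *n* = 20: 12.5%/20 = 0.625%.

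**Step 3: the treatment comparison.** Only the difference between arms matters. Suppose one arm has one to three more such subjects than the other (an assumption, since the documents give no frequency):
- Low end: 1 × 0.5% = 0.5% of the arm mean.
- High end: 3 × 0.625% = 1.875%, about 1.9%.
- No imbalance: no shift.

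**Step 4: noise or bias.** If the same incisors are unscored at visits 3 and 4, the shortfall is the same proportion of the score at both visits. It then acts mainly as extra between-subject variation. Minimization is described as balancing the number of subjects per group, and no tooth-related factor is named, so a chance imbalance in unscored incisors is possible. Nothing in the documents suggests a systematic one.

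**The case against.** The strongest reply is that the problem may never arise. The stain description names all eight incisors and says each will be scored. The gross-caries exclusion follows the plaque index and is paired with third molars, which can matter only for whole-mouth indices, so it may not have been written with stain in mind. The entrance criteria and the cited stain index are not shown, and either could make an unscored incisor rare or supply a rule for it.

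Much of this stands. The frequency is unknown and the shift in any treatment comparison is likely to be small. But the exclusion is worded generally, without limit to particular indices, and the text shown gives no fallback for stain.

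Three stronger readings are tempting, and the documents do not support them:
- A reader might infer that the stain comparison is biased by 12.5%. That figure applies to one subject with one unscored incisor; it is not a treatment effect.
- A reader might infer that taste perception cannot be analysed, because the survey is described only at visit 4 while the stated model has visit 3 and visit 4 levels. With one visit, that model reduces to a comparison by treatment and location, both of which the plan already names as factors. The survey form is not shown, so the absence of a named score cannot be counted as an error.
- A reader might infer that malodor has no data behind it. It is true that no measurement is described and that the aim in Materials and Methods omits it. But the survey items are not shown, so this is a matter for clarification and not a demonstrated flaw.

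**Conclusion.** The point holds for stain and is minor. As written, the rule understates a subject's stain by 12.5% per unscored incisor. This rests on two assumptions: that the gross-caries exclusion applies to the stain index, and that stain per tooth is the same on scored and unscored incisors. In a treatment comparison the shift is about 0.5% to 1.9% of an arm mean under an assumed imbalance of one to three subjects, and zero if the arms are balanced. With all eight incisors scored in every subject, the sum works as it stands.

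The arithmetic is certain; how often it would apply is not. No primary outcome, power figure or sample size is touched. The case for changing the rule is that the better definition costs nothing and brings stain into line with the other indices.

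**What to change.** Define the stain score as the sum of the incisor scores divided by the number of incisors scored. To keep the 0–24 scale, use eight times that mean. The cost is one line of text, with no new measurement or visit. If all eight incisors are scored in every subject, the first version only rescales the score, leaving test results unchanged, and the second reproduces the sum exactly.

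Two optional clarifications could be made in the same edit:
- State that the visit 4 taste survey is analysed by treatment and location without the visit factor, with a method suited to its response scale.
- Reconcile the outcome lists. Malodor appears only in Data Analysis and has no described measurement; patient compliance is listed as an outcome only in the aim in Materials and Methods.

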Study Protocol and Statistical Analysis Plan

Study Title:

Comparative Evaluation of SmartMouth Clinical DDS Advanced Oral Rinse and Chlorhexidine Mouth Rinse

Date:

7-13-2015

Introduction:

The primary etiology for dental caries, gingivitis, and periodontal disease is the formation of bacterial colonies on the tooth surface. An inflammatory process follows the accumulation of dental plaque resulting in gingivitis. Many studies have demonstrated that plaque-induced gingivitis can be reversed following complete plaque removal. Patients are instructed by oral health professionals to regularly and thoroughly remove plaque using a daily oral hygiene regimen. Many patients demonstrate poor compliance, possibly due to lack of motivation, dexterity, or skill. An antimicrobial mouth rinse, when used as an adjunct to daily oral hygiene routine, can be beneficial to patients by reducing plaque accumulation and gingival inflammation.

Mouth rinses with 0.2% chlorhexidine gluconate are used commonly in Europe. Numerous studies have demonstrated the antiplaque and anti-gingivitis effectiveness of this rinse. Side effects associated with this mouth rinse include tooth staining, calculus formation, and altered taste sensation. Studies have also been conducted with 0.12% chlorhexidine. These trials found the antiplaque and anti-gingivitis effectiveness is comparable to the 0.2% solution, but with diminished side effects. The 0.12% chlorhexidine mouth rinse (Peridex®) is widely used on a prescription basis in the United States.

Clinical trials have confirmed the efficacy of cetylpyridinium chloride (CPC) mouthrinses, but there is limited data comparing CPC to other antimicrobial ingredients. CPC rinses are not associated with side effects such as staining or taste alteration, and its use is well tolerated by patients. SmartMouth Clinical DDS Advanced Oral Rinse (a.k.a. SmartMouth Advanced Clinical Formula) (Triumph Pharmaceuticals, Inc., St. Louis, MO) is an over-the-counter mouth rinse formulated to reduce plaque and gingivitis and to provide long term fresh breath through the elimination and prevention of bad breath sulfur gases (Volatile Sulfur Compounds or VSC) utilizing zinc-ion technology. The active ingredient in SmartMouth Clinical DDS Advanced Oral Rinse is 0.05% cetylpyridinium chloride (CPC).

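### Does the undefined as-treated analysis leave the SM–CHX equivalence claim exposed to under-use of the rinses?

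*Combined protocol and SAP*

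**What the plan says.** Data Analysis takes intention to treat as the basis and follows with "Sensitivity analyses will be based on as treated analyses". No grouping rule, threshold, outcome or comparison is attached to that line.

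The closing paragraph of the Introduction counts compliance among the outcomes: "The outcomes included measures of plaque, gingivitis, tooth staining, calculus formation, patient compliance, and taste perception". Materials and Methods measures it ("compliance defined as percentage of product used") from rinse returned at visits 3 and 4 ("Each subject will return the unused rinse"). The outcome list in Data Analysis leaves it out: "Secondary outcome measures are tooth discoloration, taste perception, malodor and calculus". The planned repeated-measures model contains treatment, location and visit, with no term for product use.

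The paragraph on equivalence with 0.12% chlorhexidine gives a margin of 0.20, SD 0.25, 21 subjects per group, one-tailed alpha 0.05 and 81.7% power. It names no analysis population.

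**The concern.** In a superiority test, under-use usually works against the claim. In an equivalence test it can work for it: if subjects take less of two products that truly differ, their means move together. Intention to treat alone is therefore not automatically conservative for SM versus CHX.

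The as-treated line does not obviously help. In its usual sense subjects are grouped by product received. Each subject gets one coded rinse and no switching is described, so the result would hardly differ from intention to treat. If the authors meant amount used, the cut-off is unstated and could be picked after results are seen.

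The Introduction also gives some reason to expect unequal use. For the 0.2% chlorhexidine rinse it says: "Side effects associated with this mouth rinse include tooth staining, calculus formation, and altered taste sensation". It describes CPC rinses as free of staining and taste problems. The reason is modest, because the trial uses the 0.12% strength, which the Introduction calls "comparable to the 0.2% solution, but with diminished side effects".

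At stake is whether an equivalence finding could reflect poor use rather than similar products, with nothing planned to show it.

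**Working it through.** **1. The plan's own figure.** Inputs from the equivalence paragraph: n = 21 per group, SD 0.25, margin 0.20, one-sided alpha 0.05, true difference 0.
- Standard error = 0.25 × √(2/21) = 0.0772.
- Noncentrality = 0.20/0.0772 = 2.59 on 40 df; critical t = 1.684.
- One-sided power against a single bound = 81.7%, which matches the plan.
- Requiring both bounds gives 63% (90% interval) or 43% (95% interval). That is a separate matter, but it shows how little precision there is to spare.

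**2. How far under-use could move the intention-to-treat result.** Assumptions:
- SM effect at full use 0.44 (the plan's anticipated SM–placebo difference).
- CHX effect at full use 0.64, so the true difference sits exactly at the margin.
- Effect proportional to use.
- Use varies between subjects (beta distribution, SD 0.20); residual SD 0.25.

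As-used difference = 0.64 × CHX use − 0.44 × SM use:
- 80/80: 0.512 − 0.352 = 0.160
- 90/80: 0.512 − 0.396 = 0.116
- 90/70: 0.448 − 0.396 = 0.052

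Simulated chance of declaring equivalence (100,000 trials) is 11%, 23% and 44% with the 90% interval, or 5%, 12% and 24% with the 95% interval. At full use the figures are 5% and 2%. If use is all-or-none, they are only 6%, 12% and 16%, or 1%, 3% and 3%.

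These are not error rates of the planned comparison. All three as-used differences lie inside 0.20, so for the products as used, declaring equivalence is correct.

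**3. What a per-protocol test would add.** Same scenario, keeping subjects with use of at least 80% (an assumed cut-off). Mean numbers left (SM/CHX) are 12.9/12.9, 17.5/12.9 and 17.5/7.9.

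Approximate interval half-width = t × 0.25 × √(1/n₁ + 1/n₂):

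| SM/CHX use (%) | Standard error | 90% half-width | 95% half-width |
|---|---|---|---|
| Intention to treat, 21/21 | 0.077 | 0.130 | 0.156 |
| 80/80 | 0.098 | 0.168 | 0.203 |
| 90/80 | 0.092 | 0.156 | 0.188 |
| 90/70 | 0.107 | 0.184 | 0.221 |

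At the 95% level, two of the three half-widths exceed the margin of 0.20. An interval of that width cannot fit inside the margin even if the observed difference is zero.

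Simulation with truly equal products (effect 0.44 in both arms):

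| SM/CHX use (%) | Per-protocol pass, 90% / 95% | Intention-to-treat passes that fail per protocol, 90% / 95% |
|---|---|---|
| 80/80 | 25% / 9% | 65% / 83% |
| 90/80 | 35% / 15% | 49% / 70% |
| 90/70 | 15% / 4% | 76% / 90% |

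**4. Can a rule tell under-use from imprecision?** Suppose an intention-to-treat pass is called sensitive to under-use only if the per-protocol test fails and the absolute estimate rises by more than 0.05. By the 90% rule, the label fires in 43%, 49% and 62% of passes when the true difference is 0.20, and in 28%, 21% and 35% when the products are equal. The ratios are about 1.5, 2.3 and 1.8, which is weak discrimination.

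**5. Selection.** If use correlates 0.3 with better gingival scores for reasons unrelated to the rinse (an assumption), equal products would show a spurious per-protocol difference of about 0.02 at 90/80 and 0.05 at 90/70.

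**The case for a change.** The strongest case for a change is that the remedy is cheap. An undefined sensitivity analysis cannot be reproduced. A measured outcome deserves a planned report. A per-protocol result beside intention to treat is common in equivalence trials, and the data are already collected. In the varying-use scenario the per-protocol set does recover much of the true difference of 0.20: the mean estimate rises from 0.160, 0.116 and 0.052 to about 0.186, 0.165 and 0.142.

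The textual part of this stands. The term is undefined, and compliance is absent from the Data Analysis list. But Data Analysis promises one value per subject for each outcome measure, the Introduction names compliance as an outcome, and Materials and Methods defines it. A comparison of product use by arm is a fair reading of that text. An as-treated grouping can likewise be fixed before unblinding without altering the design or the primary analysis.

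The case for a per-protocol test does not stand as a needed change. Part of the fall in its pass rate is lost precision, and it fails about as readily when the products are the same. Its cut-off would have to be chosen without any figure in the documents. The largest inflation, 54% at 90/70 by the 90% rule, arises when everyone in an arm uses the same amount, and there no cut-off can help. The illustration also treats 0.44 as a full-use effect, although the plan gives it only as an anticipated difference, so under-use may be counted twice.

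**Conclusion.** No change to the plan follows. One part is missing detail: what as treated means, and where product use is reported. Analysts can settle both sensibly before unblinding, and following the plan as written gives no wrong result. The other part, a per-protocol equivalence test, is a trade-off with little gain at this sample size: with equal products it would contradict 49% to 76% of intention-to-treat passes by the 90% rule and 70% to 90% by the 95% rule. Those figures rest on assumed use rates, a use SD of 0.20, an 80% cut-off, effects proportional to use, and the plan's SD of 0.25 taken as residual. If use proves high and similar in both arms, the question largely disappears; the returned-rinse data will show whether it does.
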